#### Dual Energy X-ray Absorptiometry (DXA)

DXA scans of the lumber spine, femoral neck, and total hip will be performed at the time points specified in Section 2. Site training and qualifications, which include assessment of instruments, will be evaluated/approved by the central reader prior to screening of the first subject. Instructions on calibration and standardization of instruments and any additional required information will be specified in a manual from the central reader that will be provided to all study sites. Sites will need to obtain approval from the central reader prior to initiating study scans.

The screening DXA scan will be sent to the central reader to determine eligibility and serve as the baseline scan for subject management.

During the Treatment Periods, DXA scans will be performed for all subjects at Week 24 and will be submitted to the central reader for review and analysis. DXA scans will only be performed at the PD Visit if the subject has received study drug for at least 12 weeks.

DXA scans will be performed by qualified technologist/radiologists at the site or affiliated imaging facility using GE Lunar or Hologic equipment and per the acquisition guidelines provided by the Central Imaging Core Lab (central reader). The DXA technologist/radiologist or designee for each investigative site

should electronically submit the subject's DXA images to the central reader for review and analysis following acquisition. The central reader will be blinded to the subject's treatment assignment, but not to the corresponding time point.

Subject eligibility will be made based on the central reader review. Sites will receive reports from the central reader that detail the results (including Z-scores and bone mineral density (BMD) % change from Baseline, as applicable) of the DXA scans performed.

#### COVID-19 Pandemic-Related Acceptable Protocol Modifications

Due to the COVID-19 pandemic, if the subject is unable to come on-site or to the imaging facility, the DXA and TAU/TVU can be delayed up to 1 month from their scheduled time.

## 3.18 Dispense Study Drug

The site will dispense study drug at the time points specified in Section 2. The subject will take the first study drug dose the morning after the Baseline visit. Subjects will be instructed to self-administer their study drug throughout the Treatment Period.

## COVID-19 Pandemic-Related Acceptable Protocol Modifications

Depending on the local regulations, provisioning of study drug for direct-to-patient (DTP) and direct-from-patient (DFP) transfer because of the COVID-19 pandemic will be available per request. AbbVie will submit any required notifications to the regulatory authority as applicable.

• Sites will be responsible for meeting IRB reporting requirements and submitting the booking form to the local IRB (as applicable).

The investigator must discuss the DTP process with the subject:

- Obtain consent to provide delivery information to local courier and document this in the source.
- Obtain results of required safety procedures (e.g., urine pregnancy testing) before registering subject dispensation of study drug in IRT.
- Confirm that the subject will be available to accept delivery.
- The site will follow up with the subject after shipment is received.
- The subject should maintain the drug containers, as well as any unused drug for return to site.
- Sites will be required to retain documentation of the shipment for the IP accountability and monitoring. AbbVie will not receive subject identifying information related to these shipments, as the site will work directly with the courier.

Shipments may also include other study supplies (e.g., pregnancy tests, paper copies of PROs). Instructions will be provided by AbbVie as to how a study site can initiate a DTP shipment using a local courier selected by AbbVie to provide this service when necessary. Shipments of study drugs from the study site to a subject's home will be appropriately temperature-controlled (qualified shipper or temperature monitoring) within the labeled storage conditions. Signature is required upon delivery; due

to COVID-19 related social distancing, this may be provided by the courier after delivery. Documentation of the shipment is to be retained by the clinical site.

## 3.19 Clinical Laboratory Tests

The blood samples for serum chemistry tests will be collected following a minimum 8-hour fast prior to study drug intake. Subjects whose visits occur prior to the morning dose of study drug should be instructed to fast after midnight until the blood sample is collected in the morning and thereafter take their study drug with food. Subjects whose visits occur after the morning dose of study drug should be instructed to fast after breakfast until the study visit occurs. At the Baseline visit, a fasting blood sample should be collected. Blood samples should still be drawn if the subject did not fast for at least 8 hours. Fasting or nonfasting status will be recorded in the source documents and on the laboratory requisition. The baseline laboratory test results for clinical assessment for a particular test will be defined as the last measurement prior to the initial dose of study drug.

A certified laboratory will be utilized to process and provide results for the clinical laboratory tests. Laboratory reference ranges will be obtained prior to the initiation of the study.

Instructions regarding the collection, processing, and shipping of these samples will be provided by the central laboratory and sent to the following certified laboratory addresses:

Covance CLS [name] [name]

If a laboratory test value is outside the reference range and the investigator considers the laboratory result to be clinically significant, the investigator will:

- repeat the test to verify the out-of-range value;
- follow the out-of-range value to a satisfactory clinical resolution; or
- discontinue the subject from the study or require the subject to receive treatment; in this case, the laboratory result will be recorded as an AE.

**Table 1.** Clinical Laboratory Tests

Hematology	Clinical Chemistry (After Minimum 8-Hour Fast)	Lipid Panel (After Minimum 8-Hour Fast)
Hematocrit Hemoglobin Red blood cell (RBC) count White blood cell (WBC) count Neutrophils Bands (if indicated) Lymphocytes Monocytes Basophils (if indicated) Eosinophils (if indicated) Platelet count (estimate not acceptable)	Sodium Potassium Chloride Bicarbonate Blood urea nitrogen (BUN) Serum creatinine Glucose Calcium Total protein Albumin Total bilirubin Alanine aminotransferase Aspartate aminotransferase Uric acid	Low-density lipoprotein cholesterol (LDL-C) High-density lipoprotein cholesterol (HDL-C) Triglycerides Total cholesterol  Endocrine Hormones/Tests  Follicle-stimulating hormone (FSH) Luteinizing hormone (LH) Fasting insulin Glycated hemoglobin (HbA1c) Testosterone Sex hormone binding globulin (SHBG) Progesterone Androstenedione Anti-Mullerian hormone (AMH) Estradiol (E2) Dehydroepiandrosterone sulfate (DHEAS) Reflexive thyroid-stimulating hormone Prolactin 17-OH-progesterone (17-OH-P)
Urinalysis	Pregnancy Test	Other Tests (Screening Only)
Specific gravity Ketones Leukocytes Nitrites Protein Blood Glucose pH	Serum pregnancy Urine pregnancy	Hepatitis B surface antigen (HBsAg) Hepatitis C virus antibody (HCVAb) Hepatitis C virus RNA (HCV RNA)
Additional Blood Samples to be Coll	ected	1
Elagolix single PK sample LH/FSH single PD sample		

Optional blood samples for exploratory research and validation studies.

## COVID-19 Pandemic-Related Acceptable Protocol Modifications

If travel restrictions or other changes in local regulations in light of the COVID-19 pandemic prevent the subject from having blood drawn for laboratory testing at the study site, if possible, arrange for subjects

to have laboratory work done at a local lab, hospital, or other facility. Local lab results should be obtained along with reference ranges and kept within the subjects' source documentation. Local lab results should be reviewed by the investigator as soon as possible.

If laboratory samples cannot be collected, the site will need to reach out to the medical monitor to determine further action and if study drug should be discontinued.

Laboratory samples indicated in Table 1 will be sent to the certified central lab selected for this study. All laboratory samples listed above will be assessed using a certified laboratory selected for this study and these data will be used for data analysis. The central laboratory will provide instructions regarding the collection (including any fasting requirements), processing, and shipping of samples. Blood draws should be performed after vital signs are conducted at a visit.

Clinical chemistry samples, insulin, and lipid panel should be obtained in the morning following an overnight fast (minimum of 8 hours); however, there may be circumstances when the sample is obtained later in the day and/or not under fasting conditions. If the sample was obtained with less than 8 hours of fasting, the source documents and the lab requisition should be marked to indicate that the sample was obtained under nonfasting conditions.

The central laboratory will provide the laboratory results to the investigative site where the investigator will review, sign, and date them. For any value outside of the reference range, the investigator will review and indicate on the report if the result is clinically significant or not clinically significant. The investigator will evaluate clinically significant laboratory values per standard of care which may include repeating the test to verify the out-of-range value. Clinically significant laboratory abnormalities after randomization may be documented as AEs, depending on the investigator's interpretation.

All screening laboratory results must be reviewed prior to Baseline, including any repeated test results. Screening laboratory tests may be repeated one time prior to the Baseline Visit; however, results must satisfy entry criteria prior to randomization. Subjects should not be randomized at Baseline Visit if screening laboratory results do not meet entry criteria or the investigator assesses them as clinically significant. The most recent laboratory test results obtained prior to the Baseline Visit predose samples will serve as the Baseline for clinical assessment.

The investigator will receive sponsor-defined alerts from the central laboratory. The investigator will review the lab alerts and assess clinical significance for potential AEs.

#### Serology Testing for Hepatitis

The central laboratory will test all subjects for hepatitis B surface antigen (HBsAg) and hepatitis C virus antibody (HCV Ab) during the Screening Period. HCV RNA testing will be performed for those subjects with a positive HCV Ab. A positive HBsAg or detectable HCV RNA will exclude subject from participation. Borderline hepatitis test results should be repeated.

### Lipid Panel

The lipid panel consists of LDL-C, HDL-C, triglycerides, and total cholesterol; and should be obtained in the morning following an overnight fast (minimum of 8 hours); however, there may be circumstances when the sample is obtained later in the day and/or not under fasting conditions. If the sample was

obtained with less than 8 hours of fasting, the source documents and the lab requisition should be marked to indicate that the sample was obtained under nonfasting conditions.

## Pregnancy Tests (Serum and Urine)

Urine and/or serum pregnancy tests will be performed at the time points specified in Section 2, in all subjects regardless of sexual activity status or method of contraception, including subjects who are surgically sterilized.

The urine pregnancy test result on Baseline must be reviewed and confirmed to be negative prior to randomization.

A positive urine pregnancy test result must be confirmed with a quantitative serum pregnancy test. Study drug must not be dispensed if the subject has a positive urine pregnancy test result at any visit during the Treatment Periods (including Baseline result). The site will immediately inform the subject to discontinue study drug temporarily while the subject waits for the results of the serum pregnancy test. If a serum pregnancy test result is positive, the site should instruct the subject to complete a Premature Discontinuation visit within 2 to 7 days of study drug discontinuation.

If a subject is confirmed as pregnant, the subject will be prematurely discontinued from the study drug. For any subject who has a positive serum pregnancy test result, a transvaginal ultrasound (TVU) must be conducted as early as possible in the first trimester in order to assess the gestational age and estimated due date.

If the subject becomes pregnant at any time after randomization up through 30 days after the last dose of study drug, an ultrasound examination will be performed during the first trimester of pregnancy to assess the gestational age and estimated date of delivery. Refer to Section 4.4 for instructions on reporting of a pregnancy to the sponsor and the required follow-up on the subject's fetus, pregnancy, and infant outcomes.

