#### Pregnancy

While not an AE, pregnancy in a study subject must be reported to AbbVie within 1 working day after the site becomes aware of the pregnancy. Subjects who become pregnant after receiving at least one dose of study drug during the Treatment Period or within 30 days of last dose of study drug of the

study must be discontinued (Section 5.5). If a pregnancy occurs in a study subject, information regarding the pregnancy and the outcome will be collected.

If a subject has a positive serum pregnancy test during the Treatment Period, no additional procedures will be conducted; however, an ultrasound examination will be performed (and read locally) as early as possible during the first trimester of pregnancy to assess the gestational age and document an intrauterine pregnancy.

The pregnancy outcome of an elective or spontaneous abortion, stillbirth or congenital anomaly is considered a SAE and must be reported to AbbVie within 24 hours after the site becomes aware of the event.

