# **WEEK 24/**

### **PREMATURE**

DISCONTINUATION:

□ INTERVIEW	

AE assessment

Concomitant therapy

Birth control attestation

	
 
Contraceptive counseling/dispense nonhormonal contraceptives as necessary
 
Review e-Diary entries
 

PRO EXAM	
 
C-SSRS Since Last Visit
 
MBQ
 
Physical exam
 
Weight and waist circumference
 
Vital signs
 
Gynecological (pelvic and breast) exam
 
Acne lesion assessment and IGA
 
	
 
PCOSQ
 
PGIA and PGIH
 
MRI if required
 
Pelvic ultrasound (TVU and TAU)
 
Urine pregnancy test
 
DXA scan
 
FG Score
 

A CENTRAL LAB	
 
Endocrine hormones/test:
 
Fasting insulin
 
HbA1c
 
Androstenedione
 
AMH
 
Testosterone/SHBG
 
E2
 
Progesterone
 
	
 
Clinical laboratory test (chemistry, hematology, lipid panel, urinalysis)
 
Liver transaminases (ALT, AST) and fractionated bilirubin
 
Elagolix single PK sample
 
LH/FSH single PD sample
 
Serum pregnancy test
 
Optional biomarker sample: whole blood (DNA and RNA), serum, plasma
 

R TREATMENT	
 
Review subject dosing and perform drug reconciliation
 
	7.0

NOTE: If the Premature Discontinuation visit takes place at or before Week 12, a DXA scan would not be required.

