## 4.4 Pregnancy

Pregnancy in a study subject must be reported to AbbVie within 1 working day after the site becomes aware of the pregnancy. Information regarding a pregnancy occurrence in a study subject and the outcome of the pregnancy will be collected for any study subject with a positive serum pregnancy test after receiving at least one dose of study drug through 30 days following the last dose of study drug. In the event of a positive urine pregnancy test, while awaiting serum pregnancy test results during the Treatment Period, study drug should be temporarily discontinued.

If the subject has a positive serum pregnancy test during the Treatment or within 30 days following last dose of study drug, no additional study procedures will be conducted. However, an ultrasound examination will be performed (read locally) as early as possible during the first trimester of pregnancy to assess gestational age and document intrauterine pregnancy. The site will follow the course of the subject's pregnancy and report to the sponsor on the health of the subject and fetus at each trimester, the outcome, the newborn at the first post-delivery pediatrician visit, and the infant 6 to 12 months post-delivery. The following information should be collected: fetal outcome (e.g., spontaneous or elective abortion, live infant, or still birth), date and mode of delivery, birth weight, birth length, gender, any congenital anomaly, and medically significant complications during pregnancy or labor or delivery. For live infant births, information on the health of the infant will be collected from the first post-delivery pediatrician visit and at 6 to 12 months after delivery.

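### After a positive serum pregnancy test on treatment, two sections rule out further procedures while a third calls for a discontinuation visit whose list, DXA included, has no pregnancy exception

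*Protocol*

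**What the plan says.** Two places restrict what is done after a positive serum test.

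- Protocol 6.1, Pregnancy: "If a subject has a positive serum pregnancy test during the Treatment Period, no additional procedures will be conducted". The one examination it excepts is that "an ultrasound examination will be performed (and read locally) as early as possible during the first trimester of pregnancy".
- Operations Manual 4.4 repeats the rule and extends it past the end of dosing: "within 30 days following last dose of study drug, no additional study procedures will be conducted". It again excepts a locally read ultrasound.

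A third place gives a different instruction. Operations Manual 3.19 (Pregnancy Tests) says that after a positive serum result "the site should instruct the subject to complete a Premature Discontinuation visit within 2 to 7 days of study drug discontinuation". It also requires a transvaginal ultrasound and refers the reader to 4.4 for reporting and follow-up.

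Two places set conditions for DXA at the Premature Discontinuation visit.

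- Operations Manual 2.2, note to the Week 24/Premature Discontinuation list: "If the Premature Discontinuation visit takes place at or before Week 12, a DXA scan would not be required".
- Operations Manual 3.17: "DXA scans will only be performed at the PD Visit if the subject has received study drug for at least 12 weeks".

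**The concern.** The same event, a positive serum test on treatment, leads to instructions that cannot all be followed as written. If nothing but an ultrasound is done, the visit called for in 3.19 is not carried out as listed. If the visit is carried out as listed, the restriction in 6.1 and 4.4 is broken.

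This is a question of subject safety and site conduct. The discontinuation list includes X-ray imaging, and nothing in the list or its DXA conditions removes that item for a pregnant subject. Protocol 5.9 prohibits deviations except to eliminate an immediate hazard, so a site that picks one instruction departs from another whichever it picks. Pregnancy is also foreseeable here: the clinical hypothesis in Protocol 2.1 includes improved ovulation, and Operations Manual 3.9 has subjects counseled that the study drug is not a contraceptive.

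**Working it through.** The main point is textual, so the check sets the sections side by side for one case: a subject in the Treatment Period whose serum test is positive.

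1. **Protocol 6.1 and Operations Manual 4.4.** No further procedures, with an ultrasound as the only examination excepted. Neither section mentions a discontinuation visit.

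2. **Operations Manual 3.19.** A Premature Discontinuation visit 2 to 7 days after stopping drug. No reduced form of that visit is defined for pregnancy here, in 2.2 or in Appendix D.

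3. **Operations Manual 2.2 and Appendix D.** The Week 24/Premature Discontinuation list contains interviews, questionnaires, physical and gynecological examinations, pelvic ultrasound, MRI if required, DXA, central laboratory samples and drug reconciliation. Only the ultrasound matches the exception in step 1.

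4. **DXA.** Section 3.19 does not name DXA. The scan enters through the general list, subject to the conditions in 2.2 and 3.17. Since neither mentions pregnancy, a subject past Week 12 with at least 12 weeks of drug still has DXA on her list.

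5. **Protocol 5.6.** Subjects who stop study drug early continue all scheduled visits unless they withdraw consent. There is no pregnancy exception, and 3.17 schedules a Week 24 DXA for all subjects. Section 3.19 describes a confirmed pregnancy as discontinuation from study drug, so 5.6 could be read as applying. That gives a third possible path.

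The two DXA conditions also differ from each other, and a short calculation shows where.

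- Inputs: the first dose is the morning after Baseline (Operations Manual 3.18), so it falls on day 1 after Baseline. Week 12 is 12 × 7 = day 84. Visits after Week 4 may move by 3 days (2.2). A serum test is scheduled at Week 12 (2.2). Duration is last dose date minus first dose date plus 1 (SAP 6.0).
- Assumptions: the last dose is taken on the day of the Week 12 visit, no doses were interrupted, and Week 12 in the DXA note means day 84.
- Visit on day 84: exposure is 84 − 1 + 1 = 84 days, which is 12 weeks. The discontinuation visit falls on days 84 + 2 = 86 to 84 + 7 = 91, after Week 12. Both conditions leave DXA on the list.
- Visit on day 81 (84 − 3): exposure is 81 − 1 + 1 = 81 days, short of 84. The discontinuation visit falls on days 83 to 88. On days 85 to 88 the timing waiver in 2.2 does not apply, while 3.17 says the scan is not performed.

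Treatment interruptions would separate the two conditions further. A pregnancy exception added to only one of them would leave the other standing.

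**The case against.** The strongest reply is that the sections can be harmonized. The word *additional* could mean beyond the close-out visit. Much of that visit is administrative or safety follow-up, such as adverse events, concomitant therapy and drug return. A rule written for pregnancy, and stated twice, can also be taken to limit a checklist written for every early discontinuation. Section 3.19 itself points to 4.4, and Protocol 5.9 holds the investigator to all protocol requirements, so a careful site may well omit the scan.

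Part of this stands. These safeguards mean the documents support saying only that a site *could* perform the scan. But 6.1 and 4.4 do not except a close-out visit; they except the ultrasound. On the harmonized reading, moreover, the whole discontinuation list applies and DXA stays on it.

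A reader might also infer more than the documents support:

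- **That they expressly order DXA in pregnancy.** They do not. The step is an inference from a general list.
- **That visit timing is the only limit on DXA.** Section 3.17 adds an exposure limit.
- **That every positive serum test is affected.** A positive test after the last dose, or at the Week 24 visit itself, triggers no separate discontinuation visit.
- **That half of the subjects are exposed to the DXA conflict because Week 12 is the midpoint of 24 weeks.** That is calendar time, not a count of subjects.
- **That the restriction was written because of radiation.** No reason for it is given.

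**Conclusion.** The inconsistency is real and should be corrected. For a positive serum test on treatment, Protocol 6.1 and Operations Manual 4.4 allow only an ultrasound. Operations Manual 3.19 calls for a visit whose list goes well beyond that and has no pregnancy exception.

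The number affected cannot be stated. About 130 subjects are planned, dual nonhormonal contraception is required of those not exempt (Protocol 5.2), and the number may be small. Efficacy analyses are untouched, so the weight of the point lies in subject safety and in clear instructions to sites.

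The DXA part rests on the visit list applying as written, because no reduced version exists. This review takes no position on which instruction is clinically right.

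**What to change.** Reconcile Protocol 5.6, Protocol 6.1 (Pregnancy), Appendix D, and Operations Manual 2.2 (Week 24/Premature Discontinuation), 3.17 (DXA), 3.19 (Pregnancy Tests) and 4.4. One statement should say which Premature Discontinuation visit assessments do and do not apply after a positive serum pregnancy test, and whether the continued visits in 5.6 apply to such a subject. Carry it into the visit table and into both DXA conditions, and align those two conditions with each other. The sponsor's medical team decides the content.

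The cost is wording in the protocol and Operations Manual, with the ethics review that any amendment needs (Protocol 8.1). Sample size, data collection for other subjects and the SAP's efficacy analyses do not change.
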